Noni (Morinda citrifolia) is included in the listings of traditional medicines of Native Hawaiians, other Pacific Islanders, and Asian populations, and has been used to treat various diseases for centuries [McClatchey, 2002]. Morinda citrifolia has been found previously to have a significant antioxidant activity. Present-day commercially available Noni is reported to be composed of over 140 chemical components, including flavonoids, coumadins, anthraquinones, and iridoid glycosides. Three compounds: asperulosidic acid (an iridoid glycoside), damnacanthal (an anthraquinone) and scopoletin (a coumadin), have

in vitro cellular/molecular effects possibly relevant to the inhibition of cancer development and progression. Asperuloside is reported to suppress tumor-promoting phorbal ester (TPA) - or epidermal growth factor (EGF)-induced cell transformation and associated activating protein-1 (AP-1) transcription factor activity [Liu & Bode et al., 2001]. Damnacanthal, which has strong tyrosine kinase-inhibitory effects, stimulates ultraviolet-induced apoptosis in ultraviolet-resistant human UVr-1 cells and has been shown to induce normal phenotypes in ras-transformed cells [Hiwasa, Arase, Chen, Kita, Umezawa, Ito, & Suzuki, 1999]. Scopoletin has antiproliferative effects and can induce apoptosis of human androgen-independent prostate cancer, PC-3 cells [Liu & Zhang et al., 2001].

Clinical Experience: Noni Extracts and Cancer

In a phase I study involving 51 patients with advanced cancers enrolled at seven dose levels of Noni extract, the maximum tolerated dose was six capsules four times daily (12 g). Although no dose-limiting adverse events were found, seven of eight patients at the next level (14 g), withdrew due to the challenges of ingesting so many capsules. Furthermore, there was no evidence to indicate an optimal therapeutic dose or dosing interval [Issell, 2008]. In a study in which ~6-8,000 mg of Noni extract was consumed daily, a significant reduction in systemic inflammatory markers were noted [Akihisha, 2007]. Evidence from these clinical trials, as well as the preclinical data on Noni, attest to the safety (i.e., there was no known toxicity) and efficacy of modulating key cellular and molecular pathways that could be involved in prostate cancer progression, thus a confirmatory Phase II clinical trial using Noni extract (6,000 mg/day) is the logical next step. Note - there was no evidence that Noni could accelerate tumor growth.

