PATIENT ENROLLMENT CRITERIA

The criteria for inclusion or exclusion of study participants.

Inclusion Criteria

- 1. Men with a diagnosis of very low risk (<5% risk of disease relapse after primary treatment, criteria; cT1c, Gleason ≤6, PSA < 10 ng/mL, fewer than 3 positive biopsy cores ≤ 50% cancer in any core, PSA density < 0.15 ng/mL/g); low risk (10% risk of disease relapse after primary treatment, criteria; cT1-2a, Gleason ≤6, PSA < 10 ng/mL) prostate cancer
- 2. Very low risk and low risk groups will be confirmed by Oncotype DX prostate cancer test and provided a Genomic Prostate Score (GPS)
- 3. 55 years of age and older (\geq 55 years) at the time of informed consent

- 4. No evidence of extraprostatic disease on pelvic MRI
- 5. No baseline PT/PTT abnormalities, coagulopathies, or who are on any blood thinners.
- 6. ECOG performance status 0-2 (Appendix A)
- 7. Participants must have normal organ and marrow function as demonstrated by the following parameters being:
 - a. complete blood count with differential (CBC \overline{c} diff) no clinically significant findings
 - b. complete metabolic profile (CMP) no clinically significant findings
- 8. Willing to comply with proposed visit and treatment schedule
- 9. Able to understand and willing to sign a written informed consent document

Exclusion Criteria

- 1. Prior history of treated prostate cancer
- 2. Concomitant use of medications that are known CYP3A4 substrates
- 3. Use of medications or supplements that are known to affect PSA within 30 days prior to informed consent, including toremifene citrate, finasteride, testosterone, dehydroepiandrosterone (DHEA) or other testosterone-like supplements. No dutasteride within 90 days prior to first noni dose (**Appendix B**)
- 4. Consumption of any concomitant nutritional, herbal supplements, and antioxidants should be taken under the discretion of the investigator. The following foods/supplements are prohibited at least 7 days prior to initiation of and during study treatment:
 - St. John's wort or hyperforin (potent CYP3A4 enzyme inducer)
 - Grapefruit juice (potent cytochrome P450 CYP3A4 enzyme inhibitor)
- 5. Use of any blood thinners.
- 6. Consumption or use of any Noni or Noni-containing products
- 7. History of renal or hepatic disease, including history of hepatitis B or C. Uncontrolled intercurrent illness including, but not limited to, ongoing or active infection, symptomatic congestive heart failure, unstable angina pectoris, cardiac

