arrhythmia, or any psychological, familial, sociological or other concomitant condition that would not allow adequate compliance with the study protocol

- 8. History of allergic reactions attributed to Noni or other compounds of similar chemical or biologic composition to Noni, or the inactive components present in Noni capsules.
- 9. Participation in any other interventional study or use of any other investigational agents within 30 days prior to study entry

Inclusion of Women and Minorities

Members of all races and ethnic groups are eligible for this trial. Since this is an investigation targeting men with prostate cancer, women are not eligible for the study.

Recruitment Plan

Men who were diagnosed with very low risk or low risk prostate cancer, confirmed by Oncotype Dx Prostate Cancer Test, within the past12 months will be invited to participate in this trial. After signing an informed consent form patients will be screened for eligibility. UHCC will advertise in local newspapers and community organizations to widen the recruitment/catchment areas. Working with community physicians and oncologists is the most direct and effective approach, and we will target the primary care physicians and urologists as our primary source to recruit subjects, including racial/ethnic minorities, for this clinical trial.

TREATMENT PLAN

Dose Regimen and Dose Groups

This is a phase II study of Noni extract in prostate cancer. Intervention will be administered on an outpatient basis. Drug will be dispensed by clinical research staff at each of the participating investigational sites and self-administered by the participants. Subjects participating in the study will be receiving a total daily dose of 6,000 mg/day (4 capsules with breakfast, 4 capsules with lunch and 4 capsules with dinner). Six bottles each containing 60 capsules will be dispensed to each participant upon enrollment. Then 12 bottles (at 30-day visit) and 18 bottles (at 3, 6 and 9 month visits) will be dispensed to each participant. Timing of next study visit schedule will be taken into consideration when drug is dispensed to ensure an adequate supply of drug until next visit. On the day of a study visit, capsules should be taken within 4 hours of visit and blood draw for required lab work. If the patient is scheduled to come in the afternoon, dose should be taken with lunch.

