Study drug administration will continue from the time of enrollment until the time of repeat biopsy (12 month), disease progression or until off study (see *CRITERIA FOR EVALUATION AND ENDPOINT DEFINITION*). The planned/maximum duration of

treatment is one year. A total of 72 bottles of study drug (4,320 capsules) will be distributed per subject over the 12-month treatment period.

Contraindications

Noni is contraindicated in subjects who are hypersensitive to Noni products or any of the inactive ingredients found in the drug product capsules.

Concomitant Medications

During study participation, subjects may not consume any additional Noni extract. Subjects consuming the equivalent of an additional 1,000 mg of Noni extract will be considered noncompliant, and will have the study requirements re-explained to them up to two separate visits. Persistent non-compliance for 6 months may result in removing the subject from study.

Participants may not take anticoagulants, such as heparin, or Coumadin or steroid hormones or medications, which have known impact on PSA. If a subject begins taking these medications after being enrolled, they will be withdrawn, taken off study drug and replaced.

A list of supplements and medications to avoid is provided in **Appendix B**.

All medications (prescription and over-the-counter), vitamin and mineral supplements, nutritional supplements and/or tea consumption by the participant following signing of the informed consent will be documented on the concomitant medication CRF and will include: start and stop date, dose and route of administration, and indication. Medications taken for a procedure (*e.g.*, biopsy) will also be documented.

Dose Modifications

Subjects will be assessed clinically for adverse events during screening, prior to enrollment, at one month during intervention, quarterly during intervention, and at the end of intervention. Blood will be drawn at each of these study visits to assess for any adverse events. Any adverse events occurring during the investigation will be managed according to standard medical practice.

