AEs requiring dose suspension or permanent discontinuation of Noni extract are listed in the table below. Following any LFT elevation or INR increase, study drug will be withheld (grade 1) or permanently discontinued (grade ≥2), and liver function and PT/PTT monitored weekly until resolution to normal. Study drug may be resumed when laboratory values return to within reference range and will continue to be monitored weekly for 4 consecutive weeks. Study drug will also be permanently discontinued for grade 3 and 4 AEs, unless clearly not related to therapy. For grade 3-4 AEs not related to Noni extract,

we will suspend the study drug, and notify the site investigator and study PI. Noni extract may be reintroduced if AE resolves within 3 weeks.

Adverse events affecting LFT and/or PT/PTT levels will be monitored weekly until AE resolves. There are no reductions in the Noni extract dose; if AEs occur that require suspension of drug administration, the dose will remain the same once treatment resumes. Subjects who have had an interruption of intake of more than 30 calendar days may be withdrawn from the study at the discretion of the investigator. Subjects who have an unresolved AE at the time of withdrawal from study treatment will continue to be followed until resolution of the event, if possible. If an AE persists for more than 30 days after a subject goes off study, the subject will be referred to his personal physician.

Rules for Dose Suspension and Discontinuation

Event ¹	Action
Grade 1 LFT ² elevation	Suspend study drug; notify site investigator and study PI. Perform at least weekly LFTs until recovery to normal; study drug may be reintroduced if recovery occurs ≤ 2 weeks after drug discontinuation, with approval of the study PI and site investigator. After reintroducing drug, perform at least weekly LFTs. Any elevation of LFTs after drug discontinuation will results in permanent discontinuation of drug.
Grade ≥2 LFT elevation	Permanently discontinue study drug; notify site investigator and study PI. Monitor at least weekly until recovery to normal.

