- Six bottles (60 capsules per bottle) of study agent will be dispensed. The Study drug will be dispensed only to eligible patients under the supervision of the investigator or identified sub investigator(s).
- The appropriate study personnel will maintain records of study drug receipt and dispensing. The subject will be provided with logs for recording study agent during the subsequent month of treatment (**Appendix F**).

Evaluations during Study Intervention Months 1, 3, 6, 9:

Procedures followed during the visits while on study intervention are described below. Visits should take place within ± 7 days of the noted 1, 3, 6 and 9 month visits.

- At each clinic visit the research staff will assess compliance (pill count) review and collect the study agent log (**Appendix F**). All symptoms experienced by the patient and any concomitant medications taken will be recorded on the appropriate CRF and clinic notes and study logs will be entered into the subject's folder as source documents.
- Serum PSA will be drawn at 3, 6 and 9 months. Note a 30% increase in serum PSA over baseline PSA would trigger counseling to the patient regarding the need of a repeat biopsy sooner than 12 months.
- CBCc diff and CMP will be performed at screening, 3, 6, and 9 months. PT/PTT will also be monitored at each study visit. If medically indicated, blood will be drawn for hepatic function panel.
- Study blood will be collected at 6 and 9 months for banking and 3, 6, 9 months for scopoletin levels.
- LUTS score will be assessed using the AUA BPH Symptom Score Questionnaire and all patients will complete the UCLA QoL questionnaire.
- Study requirements will be reviewed with the subject.
- Counted medication will be returned to study participants and study drug will be dispensed as needed, to ensure adequate supply until the next clinic visit.
- The patient will be provided with new logs for recording study agent intake and reminded to note any signs and symptoms and concomitant medications.

Evaluations at Completion of Study Intervention (12 months)

The following procedures will be performed at the completion of the planned intervention period (12 months) or, when possible, upon early discontinuation of study agent or early study termination.

• A limited physical exam will be performed (weight, vital signs, anthropometric measurements).

- Blood will be drawn for serum PSA, PT/PTT, CBC, CMP, plasma scopoletin analysis and serum banking.
- A DRE will be performed.

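### Minor safety improvement: add a metabolic panel to the month-1 blood draw, because transaminases and bilirubin are first scheduled on treatment at month 3

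*Combined protocol and SAP*

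**What the plan says.** **Schedule.** Under Evaluations during Study Intervention Months 1, 3, 6, 9: "CBCc diff and CMP will be performed at screening, 3, 6, and 9 months". PT/PTT is done at every visit, and a hepatic panel may be drawn earlier for clinical cause. Month-12 chemistry is listed separately. Blood Collection Schedule and Purpose puts the CMP at screening and months 3, 6, 9 and 12, adds month 1 only for PT/PTT, and gives a month-1 total of 5 ml. Footnote 1 there says that the CMP covers the hepatic panel, including direct bilirubin.

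**Purpose of the draws.** Dose Modifications lists the one-month visit among the adverse event assessments and says: "Blood will be drawn at each of these study visits to assess for any adverse events". It names no analytes.

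**Dose rules.** The same section states: "Following any LFT elevation or INR increase, study drug will be withheld (grade 1) or permanently discontinued (grade ≥2". After a restart, the man "will continue to be monitored weekly for 4 consecutive weeks". The grade 1 row of Rules for Dose Suspension and Discontinuation says: "Perform at least weekly LFTs until recovery to normal". It then asks for at least weekly tests after reintroduction and gives no end date. Footnote 2 to that table includes PT/PTT among the liver function tests.

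**Background risk.** Clinical Experience: Noni Extracts and Cancer says "there was no known toxicity". Inclusion criterion 7b requires "complete metabolic profile (CMP) no clinically significant findings", and exclusion criterion 7 bars any history of hepatic disease.

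**The concern.** The liver rules act from grade 1, a level at which a man may well feel nothing. A rule of that kind works only if someone measures. Until month 3 no scheduled transaminase or bilirubin result exists for it to act on, and a for-cause panel would not be triggered in a man without symptoms or signs. At the 30-day visit he is bled for safety and given a further supply ("Then 12 bottles (at 30-day visit"), which covers the next 60 days at full dose.

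At stake is the safety of a man with a silent elevation at month 1, who would stay on 6,000 mg/day until the month-3 result. The quarterly interval after month 3 is not in question.

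**Working it through.** **1. Reproduce the blood table.** Tube volumes from Blood Collection Schedule and Purpose: CMP with PSA 10 ml (about 5 ml each), CBC 5, scopoletin 5, banking 5, PT/PTT 5.

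| Visit | Sum | Stated total |
|---|---|---|
| Screening | 10 + 5 + 5 (CMP/PSA, CBC, PT/PTT) | 20 ml |
| Enrollment | 5 + 5 (scopoletin, banking) | 10 ml |
| Month 1 | 5 (PT/PTT) | 5 ml |
| Month 3 | 10 + 5 + 5 + 5 | 25 ml |
| Month 6 | 10 + 5 + 5 + 5 + 5 | 30 ml |
| Month 9 | 10 + 5 + 5 + 5 | 25 ml |
| Month 12 | 10 + 5 + 5 + 5 + 5 | 30 ml |

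All totals match. The 5 ml at month 1 leaves no room for a chemistry tube. The chemistry row of the Schedule of Events is damaged in the available text: even its screening mark is missing, although a screening CMP is required. It is consistent with this reading but adds little support.

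**2. Timing.** Month 1 is day 30 (the plan calls it the 30-day visit), with a window of 23 to 37. Month 3 is about day 91, with a window of 84 to 98.
- Nominal gap: 91 − 30 = 61 days.
- Shortest: 84 − 37 = 47 days. Longest: 98 − 23 = 75 days.
- Result turnaround t applies to both visits and cancels: (91 + t) − (30 + t) = 61.

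**3. Planned exposure at the first check** (6 g/day): 91 × 6 = 546 g now, 30 × 6 = 180 g with a month-1 panel. The month-1 supply is 12 × 60 = 720 capsules, or 720 / 12 = 60 days.

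**4. Interval from the screening panel.** Enrollment may follow screening by up to 4 weeks, so the interval to the first on-treatment panel can reach 28 + 91 = 119 days (28 + 98 = 126 at the window edge). Later panels are about 91 days apart.

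**5. Cost for every man.** Scheduled blood: 20 + 10 + 5 + 25 + 30 + 25 + 30 = 145 ml, rising to 145 + 5 = 150 ml. Scheduled on-treatment panels go from 4 to 5 per man, or 30 × 4 = 120 to 30 × 5 = 150 in all.

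**6. Follow-up cost for a man with a grade 1 result.**
- Under the Dose Modifications text: 1 to 2 weekly tests to recovery plus 4 after restart, 5 to 6 in all.
- Under the table, which sets no end: restart by day 30 + 14 = 44 leaves (365 − 44) / 7 ≈ 46 weekly tests.
- If the same elevation would have been found at month 3, restart by day 91 + 14 = 105 leaves (365 − 105) / 7 ≈ 37. The increment is then about 46 − 37 = 9 tests under the table, and none under the text.
- The documents give no grade 1 rate. If it is assumed to be 2% to 10%, 30 × 0.02 = 0.6 to 30 × 0.10 = 3 men are affected, and the text reading gives 0.6 × 5 = 3 to 3 × 6 = 18 unscheduled tests.

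**The case against.** The strongest reply is that this is a preference. No rule is broken, and a draw that already exists could justify adding almost any test. The protocol counts PT/PTT as a liver test, so month 1 has one. The phase I study of 51 patients found no dose-limiting events, and its maximum tolerated dose was 12 g/day, twice the dose used here. Men with past liver disease are excluded and screening chemistry must be clean. An early draw limited to clotting may be deliberate, given the coumadins reported in the product and the bar on blood thinners; that is an inference.

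Most of this stands, and it is why the point is minor. It does not remove the point, because the panel requested is the one that the plan's own stopping rule needs. PT/PTT gives no transaminase or bilirubin value. The phase I summary reports neither liver chemistry nor duration of exposure.

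A reader might infer stronger claims that the documents do not support:
- **That the plan contradicts itself.** The Dose Modifications text promises blood at the one-month visit but names no panel, and a PT/PTT draw satisfies it.
- **That liver injury is likely in the first month.** Nothing in the documents shows this.
- **That the change is free of consequences for the trial.** More testing under a grade 1 rule can produce more suspensions and stops. Men who stop early are replaced, so it could slightly change who supplies the paired biopsies for the Genomic Prostate Score.

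**Conclusion.** The point holds as a minor, cheap improvement to safety monitoring. One panel is absent at one visit, which leaves the liver dose rules without a scheduled transaminase or bilirubin result until about day 91. For a man with a silent elevation at month 1, action could come about 61 days earlier, with a range of 47 to 75 days. That figure is the spacing between visits; it is not a measured benefit. It assumes that the elevation is already present at month 1 and that nothing prompts a for-cause panel. How many men this would concern cannot be estimated from the documents. N, alpha and power are untouched.

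**What to change.** Add a CMP with direct bilirubin, as already defined in the protocol, to the month-1 draw, and apply the existing dose rules when the result returns. Four places need to agree:
- Schedule of Events: mark month 1 in the chemistry row, with a footnote limiting it to the CMP.
- Visit text: list the CMP at months 1, 3, 6 and 9.
- Blood collection table: change the month-1 total from 5 to 10 ml.
- CMP paragraph heading: months 1, 3, 6, 9 and 12.

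It would help to settle in the same amendment whether weekly tests after restart end at 4 weeks or continue, since that drives most of the follow-up cost.

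**Cost.** No new visit or venipuncture is needed: one tube per man, about 30 panels plus one per replacement. Men with a grade 1 result incur the weekly follow-up shown above, part of which would arise anyway after a month-3 detection. A man who does not recover within 2 weeks, or who has grade 2 or higher, stops drug and is replaced. Each replacement takes about 0.5 to 1 month at 1 to 2 patients per month. The protocol must be amended, and any change to the consent form needs ethics board approval.

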Appendix FMedication Log

OBJECTIVES

Primary

To evaluate the Genomic Prostate Score (GPS, and associated gene expression changes) in prostatic tumors in men treated with Noni extract (6,000 mg/day) for one year following the diagnosis of very low risk or low risk prostate cancer.

To assess the rate of disease progression of prostate cancer at one year in men treated with Noni extract following the diagnosis of very low risk or low risk prostate cancer.

Secondary

Evaluate effects of Noni extract on serum PSA (*i.e.*, serum PSA doubling time) in men diagnosed with very low risk or low risk prostate cancer.

Evaluate the tolerability of Noni extract in men diagnosed with very low risk or low risk prostate cancer.

Explore the fundamental molecular pathways contributing to the activities associated with Noni extract in the prostate cancer (*e.g.*, angiogenesis (CD34), cell proliferation (Ki-67) and apoptosis (TUNEL) in prostate tissue biopsy samples).

Evaluate the effect of Noni extract on lower urinary tract symptoms (LUTS) and quality of life (QoL) in men diagnosed with very low risk or low risk prostate cancer.

Create a specimen repository (serum and prostate biopsies) to assess other genetic or environmental factors that may influence incidence and progression of prostate cancer, and to test future hypotheses related to prostate cancer.

BACKGROUND

Disease Background

Prostate cancer is the most common malignancy affecting men with an estimated 232,090 cases per year in the United States [Siegal, 2015]. Despite the high incidence, disease related mortality statistics are quite favorable compared to other cancers. Less than one third of men diagnosed with prostate cancer will die of disease making it considerably less lethal than lung and colorectal cancer which rank first and second in terms of cancer related deaths [Siegal, 2015]. The high proportion of PSA-detected cancers in current clinical practice is largely responsible for this phenomenon since patients with early prostate cancer are now diagnosed at a lower tumor stage and grade compared to in previous years. While this may allow for earlier curative therapy of potentially life threatening disease, it also identifies a large group of patients with a relatively low risk of disease relapse in whom radical therapy may be unnecessary and harmful due to its associated morbidity and costs.

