- The research staff will collect the investigational agent intake log, review signs and symptoms, and concomitant medications. All symptoms and concomitant medications will be recorded on the appropriate CRF and clinic notes and study logs will be entered into the subject's folder as source documents.
- A repeat prostate biopsy will be performed (12 core biopsy) and tissue / slides sent for assessment by Oncotype DX Prostate Cancer Test.
- Finally LUTS score will be assessed using the AUA BPH Symptom Score Questionnaire and all patients will complete the UCLA QoL questionnaire..
- Remaining study medication will be collected, counted, and appropriately stored while awaiting destruction.

Post-intervention Follow-up Period

Subjects will be contacted by telephone 7+/-3 days after discontinuing study agent to capture any signs and symptoms occurring since stopping the study drug and changes to concomitant medications. The subject is considered off study after the repeat biopsy, other end-of-intervention procedures, and final telephone contact are completed.

METHODS FOR CLINICAL PROCEDURES

Prostate Biopsy

Prostate tissue will be obtained and evaluated by a pathologist affiliated with the UHCC. Representative slides from the initial biopsy and from the biopsies obtained after treatment are required for analysis. At least eight (8) core biopsies will be obtained. Formalin-fixed paraffin-embedded prostate biopsy specimens from all patients included in this study will be performed at each site, where original slides will be stained with hematoxylin and eosin (H & E). The H&E stained sections will be evaluated by light microscopy for presence of prostate cancer by a pathologist with genitourinary experiences. Then if not previously performed, the biopsy paraffin blocks will be sent to Genomic Health to undergo Oncotype DX Prostate Cancer Test.

Blood Draw

Non-fasting blood samples will be drawn following standard institutional procedures. The amount of blood to be collected and the types of tubes is listed under section BLOOD COLLECTION SCHEDULE AND PURPOSE.

Anthropometric Measurements

Anthropometric measurements such as participant's height and weight will be performed at screening/pre-enrollment and post-intervention.

Page 24 of 38

Collection of AE and Concomitant Medications Information

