Clinical records for all participants, including CRFs, all source documentation (containing evidence to study eligibility, history and physical findings, laboratory data, results of consultations, etc.), as well as IRB records and other regulatory documentation will be retained by the each site investigator in a secure storage facility in compliance with HIPAA, OHRP, FDA regulations, and ICH requirements unless the standard at the site is more stringent for a minimum of two years. The sponsor will be notified prior to the planned destruction of any materials. The records should be accessible for inspection and copying by authorized persons of the Food and Drug Administration.

STATISTICAL CONSIDERATIONS

Sample Size

A number of methods have been developed to extract useful and robust information from genomic data sets. However, attention also has to be paid to the experimental design before the investigator completes the experiment. One of the principal limitations of previous molecular profiling studies is the relatively low numbers of samples analyzed. We needed to estimate the sample size requirements necessary to satisfy a specified false discovery rate and power given various biological and experimental variations. We estimated variance based on previous biomarker work. Sample size for this study was estimated according to equation

$$n = \frac{\sigma^2 (Z_{1-\alpha/2} + Z_{1-\beta})}{(\mu_1 - \mu_0)^2}$$

 $n = \frac{\sigma^2 (Z_{1-\alpha/2} + Z_{1-\beta})^2}{(\mu_1 - \mu_0)^2}$ where σ^2 is the variance of the gene expression, $Z_{1-\alpha/2}$, $Z_{1-\beta}$ are the $(1-\alpha/2)$ th, $(1-\beta)$ th quantile of the standard normal distribution respectively, with α being the type I error and β being the type II error. All signal values were log2

transformed. Variance was calculated for each protein. The 90th percentile variance value (3.94) was chosen be the σ^2 in equation. In order to detect a 2-fold change in the expression level, $(\mu_1 - \mu_0)^2$ in equation will be 1. We used 0.05 as the significance level. The estimated sample size is 30 for 80% power. Each patient will have 2 sets of genomic data (baseline and 12 months) collected over the course of the study to monitor a unique genomic signature associated with Noni extract in very low risk or low risk prostate cancer. The accrual rate is expected to be approximately 1 to 2 patients / month. Thus, it is expected to take about 15-30 months to accrue the 30 patients.

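### Men who stop drug early go off study after one telephone call, so those who have not progressed get no one-year progression status and no later LUTS or QoL

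*Combined protocol and SAP*

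**What the plan says.** - **Timing of the closing assessments.** Under Evaluations at Completion of Study Intervention (12 months), they are done "at the completion of the planned intervention period (12 months) or, when possible, upon early discontinuation of study agent or early study termination". They include PSA, DRE, a 12-core biopsy with Oncotype DX, LUTS and QoL. The month-12 column of the Schedule of Events also covers early termination.
- **Exit.** Under Post-intervention Follow-up Period, a call 7 ± 3 days after the drug is stopped asks about symptoms and concomitant medications. Then: "The subject is considered off study after the repeat biopsy, other end-of-intervention procedures, and final telephone contact are completed". Off Study Criteria list adverse events, concomitant medication and non-compliance as reasons to leave. For treated men they ask only that post-intervention procedures be completed as far as possible. The visits at months 1, 3, 6 and 9 are described for men on intervention.
- **Objective.** A primary objective is "To assess the rate of disease progression of prostate cancer at one year in men treated with Noni extract". LUTS and QoL are scheduled through month 12.
- **Definitions.** Progression of Disease ties histological progression to the 12-month rebiopsy. It requires at least three PSA measurements over at least six months for PSA progression.
- **Replacement.** Men who stop before 12 months for reasons other than progression are replaced, and so are men without paired biopsies. For anticoagulants and medicines that affect PSA, Concomitant Medications says: "If a subject begins taking these medications after being enrolled, they will be withdrawn, taken off study drug and replaced".
- **Evaluability.** Primary Endpoint counts any eligible man with at least one dose and a post-treatment biopsy as evaluable for GPS. The synopsis describes the gene-expression endpoint as measured after 12 months of intervention.

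**The concern.** The objective asks for progression at one year in treated men, but the plan largely equates stopping drug with leaving the study. A man who stops without having progressed is assessed around the stop, if that is possible, and then no longer observed for any efficacy endpoint. Three things are at stake:

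- The progression rate would describe men who completed 12 months plus men who progressed, not all men treated.
- LUTS and QoL after the stop are lost for every early stopper, whatever the reason.
- GPS values described as 12-month results may come from very different exposures, depending on whether the replacement rule or the evaluability rule governs the analysis.

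Information not collected before these men leave cannot be recovered at the analysis stage.

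**Working it through.** **1. The plan's own figure.** The Sample Size section states: "The estimated sample size is 30 for 80% power". Its inputs are variance 3.94, a difference of 1 on the log2 scale (2-fold), and two-sided 0.05. With the squared form of its formula, n = 3.94 × (1.960 + 0.842)² / 1² = 30.9, which rounds up to 31. The stated 30 is reproduced within one patient, and power at 30 is 78.8% by the same normal formula. This figure concerns gene expression. No sample size or precision is stated for the progression rate, LUTS or QoL.

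**2. What is collected after a permanent early stop.**

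| Item | At the stop | From the call to month 12 |
|---|---|---|
| PSA, DRE | when possible | nothing scheduled |
| Biopsy and GPS | when possible | nothing scheduled |
| LUTS, QoL | when possible | nothing scheduled |
| AEs, SAEs | yes | unresolved events followed (Dose Modifications, Follow-up of AEs, Follow-up of SAE) |

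A man who stops because of progression already has his event recorded. The missing one-year status concerns men who stop for other reasons.

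**3. The PSA criterion.** PSA is drawn at screening and at months 3, 6, 9 and 12, plus at the stop when possible. Counting only these samples:

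- Stop at month 2: screening and stop give two values, so the criterion cannot be met.
- Stop between months 3 and 6: screening, month 3 and stop can give three values. With screening up to 4 weeks before enrollment, the span is at most about one month more than the time on drug, so a stop before about month 5 falls short of six months. The exception is a man whose baseline is the permitted earlier PSA, taken within three months of enrollment.
- Stop after month 6: three values over six months are available.

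So a man who stops before month 6 will usually lack the required values.

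**4. Replaced and evaluable at once.** A man who stops at month 2 for an adverse event and is biopsied then is replaced under Replacement, yet is evaluable under Primary Endpoint. His biopsy is not a 12-month rebiopsy, so its place in the histological definition is not stated. The plan does not say whether replaced men's data are analysed.

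**5. Bounds on the progression rate.** The documents give no stop rate and no expected progression rate. Assume that 10%, 20% or 30% of the first 30 men stop without progression (m = 3, 6, 9). Each is replaced by a man who is not himself replaced, and 6 of the resulting 30 progress (observed rate 20%). The rate in all 30 + m treated men then lies between 6/(30 + m), if no stopper progresses by one year, and (6 + m)/(30 + m), if every stopper does.

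| m | Treated | Lower | Upper |
|---|---|---|---|
| 3 | 33 | 6/33 = 18.2% | 9/33 = 27.3% |
| 6 | 36 | 6/36 = 16.7% | 12/36 = 33.3% |
| 9 | 39 | 6/39 = 15.4% | 15/39 = 38.5% |

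These no-information bounds come before sampling error. For 6/30 the exact 95% interval is already 7.7–38.6%.

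**The case against.** **The bounds are extreme.** The stop rates and the 6 events are assumed, and the upper limits need every early stopper to progress within a year, although the Background describes progression in this population as rare. This stands as a caution on size: the bounds show what the data could not exclude, not what is likely.

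**The plan is not blind to early stops.** It has separate off-drug and off-study lists, and it asks for the closing assessments at the stop when possible, including LUTS and QoL. That is correct, so only later scores are lost. It does not supply a one-year status.

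**A reader might infer that progression is seen only in men who tolerate 12 months of drug.** The documents do not support this. Treatment runs until biopsy, progression or leaving the study. A 30% PSA rise triggers counselling about an earlier biopsy, and Study Design/Endpoints provides for one when indicated. Early progressors are therefore captured.

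**A reader might infer that every gap favours Noni.** This is not supported either. Early GPS biopsies would tend to dilute a drug effect. Keeping progressors while replacing non-progressing stoppers can raise the observed rate; counting stoppers as non-progressed would lower it.

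**A reader might infer that the withdrawal rule for PSA-affecting medicines selectively removes men with worsening urinary symptoms.** The documents list those medicines only for their effect on PSA and say nothing about their use for symptoms.

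**Conclusion.** The point holds. Following the plan as written leaves one-year progression status unobserved in men who stop drug for reasons other than progression, and later LUTS and QoL unobserved in all early stoppers. The GPS set is ambiguous, because the replacement and evaluability rules conflict. The GPS sample size is unaffected.

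Under the stated assumptions, missing status alone makes the one-year rate uncertain over a range of about 9 percentage points with 3 replaced stoppers (27.3 − 18.2), 17 with 6 (33.3 − 16.7) and 23 with 9 (38.5 − 15.4). The direction of bias cannot be determined from the documents. This should be corrected, but it does not invalidate the trial.

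**What to change.** 1. In Evaluations at Completion of Study Intervention, Post-intervention Follow-up Period and Off Study Criteria, separate off-drug from off-study. A man who stops drug keeps the already scheduled PSA, LUTS, QoL and progression-status assessments to month 12, unless he withdraws consent or has definitive treatment. No rule for stopping drug changes.
2. Report one-year progression with all treated men in the denominator, including replaced men. Count progressions found early as events, and give bounds for men of unknown status. State that histological status at month 12 is missing for men biopsied only at an early stop; no second biopsy is proposed.
3. Exclude PSA values taken after the start of a PSA-altering medicine from the doubling time, but keep the man for the other endpoints.
4. Report GPS by actual exposure time, with biopsies in the month-12 window shown separately from early-stop biopsies. Show biopsies done early for a PSA rise or suspected progression as well. Dropping them could remove the men who are doing worst.
5. Reconcile Concomitant Medications, Replacement, Primary Endpoint, Progression of Disease, Study Design/Endpoints and the sections in item 1 on replacement, evaluability and biopsy timing.

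The cost is an amendment, CRF wording and some off-drug visits. For replaced men, these visits come on top of their replacements' visits.
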